## Overall Strategy

We will measure respiratory function at rest, exercise tolerance during graded cycle ergometry, and ratings of perceived breathlessness during constant load submaximal cycling in all subjects before and after 1 yr. We will study 72 prepubescent obese boys (n=36) and girls (n=36) including 12 boys and 12 girls misdiagnosed with asthma (BMI > 95th percentile, but less than 150% of the 95th percentile), and 24 prepubescent normal weight boys (n=12) and girls (n=12) (BMI between 16th and 84th percentile). Recently, there has been a shift towards classifying child BMI over the 95th percentile as a percent of the 95% percentile because the statistical procedures used to generate percentile curves are not accurate at the extreme tails of BMI distribution. We have chosen 150% of the 95th percentile as a reasonable cut-off or upper-limit because it will exclude children with an average age and sex specific BMI of approximately > 35 kg/m^2 (BMI Range 33.2–36.3 in boys and 34.5–37.9 in girls), which roughly corresponds to Class II obesity in adults. Our approach will enable us to study and compare boys and girls while pubertal effects on lung function and exercise responses are minimized. Furthermore, we are **not** studying the effectiveness of the intervention stimulus, the dose response of diet and exercise, or the rate of weight loss but only the response to 1) weight loss and regular exercise or 2) continued weight gain.

### Specific Aim 1: Respiratory Function at Rest in Obese Children

**Aim 1a. Introduction: at Rest Seated Upright.** The *working hypothesis* is that childhood obesity will alter pulmonary function and breathing mechanics while seated upright but to a greater extent in obese children with respiratory symptoms misdiagnosed as asthma. The *rationale* behind the proposed research centers on the fact that nonobese children already breathe at very low lung volumes and have compliant chest walls and excess fat on the chest will push FRC to lower levels where obese children may experience breathing limitations, all because of a simple reduction in lung volume. Furthermore, we propose that obese children with respiratory symptoms misdiagnosed as asthma will have greater changes in lung volumes and/or differences in peripheral airways function (e.g., resistance or reactance or both) making them more susceptible to low lung volume breathing.

**Methodology, experimental protocol, and measurements.** The strategy will be to measure body composition and respiratory function while seated upright. Height, weight, circumference measurements (chest, waist, hip, and neck), BMI, and body composition by DEXA (e.g., %body fat, fat mass, lean body mass, & distribution of chest wall fat) will be used to characterize differences in overall body size and general fat distribution (e.g., weight-to-height, waist-to-hip ratios, android/gynoid measures, & chest wall fat distribution by segmental analysis of the DEXA scan) among groups. Baseline respiratory function tests will include spirometry before and after bronchodilators (i.e., to assess airway hyperresponsiveness), airway resistance (including impulse oscillometry system to examine central & peripheral airway function), lung volumes by plethysmography, diffusing capacity, MVV, MIP, and MEP. Participants who show clinically significant airway hyperresponsiveness (i.e., to bronchodilator or bronchial challenge) will be referred for treatment and excluded from further study (~8-9% prevalence in children, CDC). The absence of asthma will be confirmed by a negative response to spirometry before and after bronchodilator and by a negative bronchial challenge test (i.e., methacholine) in obese children with a prior diagnosis of asthma without confirmation by lung function testing.

**Expected results.** We *expect* that altered respiratory function and breathing mechanics will be both prevalent and significant in obese children, primarily a reduced FRC, which may be correlated with other obesity-related changes in body composition. Furthermore, we expect that obese children with respiratory symptoms misdiagnosed as asthma will have greater changes in obesity-related respiratory function and/or differences in peripheral airways function making them more susceptible to low lung volume breathing. We also *expect* to have a better understanding of the magnitude, mechanism, and importance of the respiratory effects in obese children and the differences (if any) between obese boys and girls.

Interpretation of results. We will interpret these results to suggest that obese children have significant obesity-related alterations in respiratory function, which predispose them to potentially clinical breathing limitations especially in obese children misdiagnosed with asthma, all through a common mechanism of low lung volume breathing. This is important knowledge for the healthcare provider who may assume obese children have mostly normal lung function and that any respiratory symptom in obese children is primarily related to asthma.

**Aim 1b.** Introduction: at Rest Lying Supine. The *working hypothesis* is that childhood obesity will alter respiratory function and breathing mechanics when lying supine. Also, we propose that obese children with respiratory symptoms misdiagnosed as asthma will have greater changes in lung volumes when supine and/or differences in peripheral airways function making them more susceptible to low lung volume breathing. The *rationale* behind the proposed research centers on the fact that excess fat on the chest wall will push FRC to extremely low levels in the obese children especially when lying supine, thus creating the potential for significant breathing limitations especially in obese children misdiagnosed with asthma. To further test the hypothesis, we will add an external weight (2.5kg) between the xiphoid process and umbilicus of supine nonobese children and measure the change in FRC. This weight is lower than the 5kg that we used in preliminary testing, and is representative of the difference in chest wall fat observed between our obese and nonobese children.

Methodology, experimental protocol and measurements. The strategy will be to measure respiratory function and breathing mechanics when lying supine at the cardiopulmonary exercise station. Baseline data will consist of 15 min of sitting upright in a chair. After obtaining a steady-state, we will measure HR, SpO2% (by pulse oximetry), PETCO2, ratings of perceived breathlessness (RPB; Borg 0-10 scale), respiratory function (FVC&IC by spirometry, FRC by helium dilution, & calculate TLC=IC+FRC) including breathing pattern and tidal flow-volume loops. Measurements will be made in duplicate, and averaged for analysis, which has worked well in preliminary studies in children. During 15 min of lying supine, we will measure the same variables in the same way as above. In nonobese children only, we will add a 2.5kg external weight between the xiphoid process and umbilicus to simulate the effects of abdominal fat on FRC and make the same measurements.

Expected results. We expect that in comparison with nonobese children many obese children will have a marked reduction in FRC when lying supine, which may be correlated with other obesity-related measures of body composition. Furthermore, we expect that obese children with respiratory symptoms misdiagnosed as asthma will have greater changes in obesity-related respiratory function when lying supine. We anticipate a decrease in FRC with the external abdominal weight in the nonobese children. We expect this change will be *qualitatively* similar to that observed in obese children. We also *expect* to have a better understanding of the importance of changes in supine respiratory function in obese children, and the differences (if any) between obese boys and girls.

Interpretation of results. We will interpret these results to suggest that obese children have significant obesity-related alterations in respiratory function when lying supine, which predispose them to potentially clinical breathing limitations, especially in obese children misdiagnosed with asthma, all through a common mechanism of low lung volume breathing. This is important knowledge for the healthcare provider who sees obese children with symptoms of orthopnea or sleep related complaints. These findings would stress the need for further clinical/physiological testing in obese children with symptoms when lying supine (i.e., more testing than simple seated spirometry).

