### **Statistical Considerations**

Co-investigator [name] (UT Southwestern Division of Biostatistics) is the statistical co-investigator on this project and has assisted in the development of the statistical plan; she will also

Total n=96	Obese	Obese misdiagnosed with asthma	Non- obese
Boys	n=24	n=12	n=12
Girls	n=24	n=12	n=12

direct the data analysis on an on-going basis.

Statistical Plan. Our plan is to complete testing in nonobese and two obese groups, boys and girls separately but concurrently. Thus, sample size calculations are based upon within-gender comparisons per allocation in table at right. In Aims 1-3, comparisons will be made between nonobese, obese, and obese children misdiagnosed with asthma within the same gender with analysis of variance models (ANOVA). Pairwise group comparisons will be made using least squares means contrasts derived from the linear models. Data transformations or nonparametric tests will be utilized as needed to meet analysis assumptions. At baseline, ISSAC and ECRHS asthma screening questionnaire scores will be compared among groups with the Kruskal-Wallis test. Comparisons for Aim 4 will be made similarly, but with the addition of repeated measurements to assess the two obese groups and the nonobese children of the same gender at baseline and at 1 year of follow-up. Additional assessments of gender effects will be performed as part of a secondary analysis, but we are not powering the study to detect interaction by gender. Alpha is set at 0.05 for ANOVA and planned contrast power (PASS 11, NCSS, LLC, Kaysville, UT), described below . Data will be analyzed using SAS version 9.4 (SAS Institute, Inc., Cary, NC).

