Aim 1. Our primary variable is FRC measured while seated upright (Aim 1a) and when lying supine (Aim 1b). Based upon our preliminary data for seated FRC (%TLC) in nonobese boys (mean± SD, 42.4±2.5) and obese boys (36.5±6.2), it is calculated that a mean difference in FRC (%TLC) of 5.1 can be detected with statistical power of 81%, alpha=0.05, pooled SD of 5.0, comparing 24 obese to 12 nonobese children or to 12 obese children misdiagnosed with asthma. Our data also show that the differences may be larger for girls than boys, so power for a test between obese girls and obese girls misdiagnosed with asthma will be at least 80%. Similarly, for children lying supine, nonobese boys have an FRC (%TLC) of 34.4±8.8 vs. 23.1±3.4 obese, a more conservative difference of 6.0 %TLC is detectable with 80% power. In our formal protocol, we anticipate being able to make precise and reproducible measurements, and have confidence that we can meet our goals with the sample size proposed. Preliminary data demonstrate that these measures and effect sizes are feasible.

Aim 2. Our primary variable is peak  $\dot{V}O_2$ . From our preliminary peak  $\dot{V}O_2$  (ml/min/kg) for nonobese (41.9±4.9) and obese boys (26.3±3.9), it is calculated that our study will yield power of 80% to detect a clinically relevant mean difference of 4.7 ml/min/kg for obese versus nonobese children or obese children misdiagnosed with asthma, anticipating smaller differences than the 16 ml/min/kg mean difference observed from our data in obese versus nonobese. Effect size estimates for girls are anticipated to be similar.

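### Aim 1a sets peripheral airway function beside lung volume as a separate explanation, but the planned group contrasts carry no lung-volume term, so a resistance or reactance difference may reflect lower FRC and not the airways

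*Combined protocol and SAP*

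**What the plan says.** Specific Aim 1, Aim 1a (Introduction) proposes that the misdiagnosed group will show "greater changes in lung volumes and/or differences in peripheral airways function (e.g., resistance or reactance or both", either of which would leave them more prone to breathing at low volumes. The rationale in the same paragraph is that "excess fat on the chest will push FRC to lower levels".

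The Aim 1a methodology measures "airway resistance (including impulse oscillometry system to examine central & peripheral airway function), lung volumes by plethysmography" in one baseline battery. It does not state the lung volume at which oscillometry is recorded, and it names no volume-corrected airway index.

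Under Statistical Considerations, Aims 1-3 compare the three groups within each gender by ANOVA: "Pairwise group comparisons will be made using least squares means contrasts derived from the linear models". No lung-volume covariate is mentioned. Aim 1 is sized on FRC alone, and no SD or target difference is given for resistance or reactance.

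**The concern.** The hypothesis has two limbs, lung volume and peripheral airways. The airway limb is read from quantities that, as general measurement knowledge, depend on the volume at which they are taken: resistance tends to rise and reactance to become more negative as volume falls. The documents state neither this dependence nor that the recording is made at the child's own resting volume, so both are assumptions here.

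If they hold, two groups with identical airways but different FRC would differ in raw resistance. The plan predicts just such an FRC difference. A plain group contrast then cannot say which limb it supports. What is at stake is the mechanistic statement about peripheral airways. It matters because Aim 1a casts airway differences as something that predisposes to low-volume breathing. A difference that merely follows from low volume would be read in the wrong causal direction.

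**Working it through.** **1. The plan's own figure.** Statistical Considerations, Aim 1, states that "a mean difference in FRC (%TLC) of 5.1 can be detected with statistical power of 81%, alpha=0.05, pooled SD of 5.0". The group sizes behind this are 24 v 12 within one gender.
- Standard-error factor: √(1/24 + 1/12) = 0.3536.
- Noncentrality: 5.1 / (5.0 × 0.3536) = 2.885.
- Two-sided power: 0.800 (two-sample t, 34 df), 0.806 (three-group ANOVA contrast, 24 + 12 + 12 − 3 = 45 df) or 0.823 (normal approximation).

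The stated 81% is reproduced, so the plan is powered to see an FRC shift of this size.

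**2. FRC shift.** The pilot values are given as "Based upon our preliminary data for seated FRC (%TLC) in nonobese boys (mean± SD, 42.4±2.5) and obese boys (36.5±6.2". The ratio is 42.4/36.5 = 1.162, with natural log 0.150.

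**3. Assumptions not in the documents.**
- Airways are identical in both groups and TLC is equal, so %TLC stands in for litres.
- Resistance varies as FRC to the power −k, with k = 1 (inverse proportion) or k = 0.5 (half as strong).
- The between-child CV of resistance is 20%, 25% or 30%.

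With k = 1, identical airways would read about 16% higher in the obese group. With k = 0.5 the excess is about 8%.

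**4. Unadjusted contrast, CV taken as total spread.** Log SD = √ln(1 + CV²), which is 0.198, 0.246 and 0.294. Noncentrality = k × 0.150 / (log SD × 0.3536), with 34 df and two-sided alpha 0.05.

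| | CV 20% | CV 25% | CV 30% |
|---|---|---|---|
| k = 1: noncentrality | 2.14 | 1.72 | 1.44 |
| k = 1: significant | 55% | 39% | 29% |
| k = 0.5: significant | 18% | 13% | 11% |

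**5. Unadjusted and adjusted, by simulation.** Here FRC varies between children with SD 5.0, and the CV is the spread beyond that due to FRC (3,000 trials per setting, nonobese 12 v obese 24).

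| | Unadjusted, CV 20% | Unadjusted, CV 30% | With log FRC as covariate |
|---|---|---|---|
| k = 1 | 43% | 25% | about 5% |
| k = 0.5 | 17% | 10% | 4-5% |
| k = 0 | 5% | 5% | 5% |

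The two readings of the CV together give about 25-55% at k = 1 and 10-18% at k = 0.5. The adjusted 5% is a best case: the simulated covariate has the correct form and no measurement error.

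**6. Obese v misdiagnosed.** If FRC were 5.1 %TLC lower in the misdiagnosed group (36.5 to 31.4, ratio 1.162), the unadjusted rates at k = 1 are 42% and 25% for CV 20% and 30%. If FRC is the same in both groups, the rate is about 5%.

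**7. Resistance multiplied by FRC.** At k = 1 this product holds about 5%. At k = 0, for nonobese v obese, it gives false positives in about 40% (CV 20%) and 25% (CV 30%) of trials, because it imports the FRC difference into the index.

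**The case against.** The strongest reply is that little hangs on this. Aim 1's primary variable is FRC, and the airway indices have no power statement or success rule. The planned interpretation already attributes the findings to low lung volume, which a volume-driven rise in resistance would fit. This stands, and it confines the point to the airway limb of the Aim 1a hypothesis. It does not remove the point, because the plan still offers the airway limb as a separate explanation and has no analysis that could separate it.

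A second reply is that the size rests on an assumed volume dependence and an assumed CV. That also stands, and the figures are illustrative. A reader might infer that low FRC is bound to produce a false airway finding. The documents do not support that: at k = 0 the error rate is nominal, and even at k = 1 with a CV of 30% most trials would show no significant difference.

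Three further inferences are tempting and should not be drawn.
- **Misdiagnosed v other obese children.** A reader might treat 5.1 %TLC as the expected gap, or add it to the pilot gap for a nonobese v misdiagnosed comparison. It is a detectable difference. No preliminary FRC is given for misdiagnosed children.
- **Aim 4.** A reader might expect weight loss to be reported as airway improvement. Aim 4's primary variables are FRC, peak VO2, RPB and EELV, and its expected results contain no airway-improvement claim.
- **Supine and exercise aims.** The airway limb recurs in Aims 1b and 3. The supine list ("respiratory function (FVC&IC by spirometry, FRC by helium dilution, & calculate TLC=IC+FRC" and related measures) and the exercise list name no resistance or reactance. A reader might conclude that seated oscillometry is the only airway evidence, but both lists include tidal flow-volume loops, and the seated battery includes airway resistance more broadly.

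Finally, adjustment may remove a real effect if an airway abnormality itself lowers FRC. That is why the unadjusted contrast must stay, and why an unadjusted-only difference should not be assigned to lung volume outright.

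**Conclusion.** The point holds in limited form. As written, the Aim 1 analysis cannot tell a peripheral airway difference from the effect of a lower FRC on resistance and reactance. With the pilot FRC ratio of 1.16, 24 v 12 children, identical airways, equal TLC and a CV of 20-30%, the unadjusted contrast would be significant in about 25-55% of trials under inverse proportionality and about 10-18% at half that dependence. With FRC as a covariate the rate is about 5%. The dependence and the CV are assumptions, and for obese v misdiagnosed children the problem is conditional on an FRC difference that the plan predicts but has no data on. The FRC comparison itself is sound on this point. It is worth correcting because the remedy is cheap and the data are already collected.

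**What to change.** In the Statistical Plan for Aim 1:

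- Report each oscillometric resistance and reactance contrast twice: unadjusted, and with measured FRC in litres and height as covariates. Prespecify the scale of each variable (the check above used resistance and FRC on the log scale).
- Claim a peripheral airway difference independent of lung volume only if the adjusted contrast supports it. Describe a difference seen only in the unadjusted contrast as not distinguishable from a lung-volume effect.
- Specific resistance or conductance may be reported as supportive. It should not be the decision criterion, because multiplying by volume over-corrects when the dependence is weak.
- If airway variables are analysed at 1 year, use the same paired reporting.

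The cost is SAP wording, one extra model per airway variable, and one or two degrees of freedom. Plethysmographic volumes are already in the battery, so no new test is needed. The downside is partial over-adjustment if an airway effect itself alters FRC; showing both contrasts lets the reader see this.

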### **Specific Aim 2: Exercise Tolerance in Obese Children**

Introduction: Exercise Tolerance. The *working hypothesis* is that respiratory effects of obesity in children will decrease exercise tolerance (i.e., decreased peak  $\dot{V}O_2$  in ml/min/kg) but **not**

cardiorespiratory fitness (i.e., normal peak  $\dot{V}O_2$  in percent predicted based on ideal body weight), except in those misdiagnosed with asthma. The *rationale* behind the proposed research centers on the fact that conventional thinking suggests that obese children are 'out of shape' or deconditioned, but when displayed appropriately, cardiorespiratory fitness will be within normal limits during graded cycle ergometry. However, in obese children misdiagnosed with asthma, cardiorespiratory fitness may be decreased also due to respiratory symptoms and/or avoidance of exercise.

Methodology, experimental protocol and measurements. The strategy will be to measure HR, BP, SpO2%, PETCO2, gas exchange ( $\dot{V}_E, \dot{V}O_2, \dot{V}CO_2$ , RER), RPB (Borg 0-10 scale), RPE (6-20 scale), and breathing mechanics (IC, EELV, EILV) including breathing pattern and tidal flow-volume loops continuously during maximal graded cycle ergometry (step increments of 10W/min) using standard methods as required for participant safety. A maximal flow-volume loop will be measured before and immediately after the exercise to assess the possibility of bronchodilation or bronchoconstriction (i.e., exercise induced airway reactivity) during exercise.

Peak exercise capacity will be evidenced by peak HR, peak work rate, peak  $\dot{V}O_2$ , and peak RER obtained during graded cycle ergometry as well as by verification at 105% of maximal work rate to exhaustion.

Expected results. We expect that in comparison with nonobese children, obese children will have decreased exercise tolerance due to increased body weight but normal cardiorespiratory fitness when peak  $\dot{V}O_2$  is properly evaluated, despite altered breathing mechanics (e.g., EELV, expiratory flow limitation) during peak exercise. However, we also expect cardiorespiratory fitness may be decreased in obese children misdiagnosed with asthma. We also expect to have a better understanding of obesity-related alterations in respiratory function during peak exercise in obese children and the differences (if any) between obese boys and girls.

Interpretation of results. We will interpret these results to suggest that obese children are not deconditioned despite significant obesity-related alterations in breathing mechanics during peak exercise, except in obese children with respiratory symptoms misdiagnosed as asthma where cardiorespiratory fitness may be reduced also. This could be due to greater breathing alterations or an avoidance of exercise. These findings are extremely important for healthcare providers who examine fitness and associations with chronic disease in obese children, and prescribe weight loss and exercise programs.

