**Aim 4.** Primary variables for Aim 4 are change in FRC at rest, peak  $\dot{V}O_2$ , RPB, and EELV during constant load exercise from before to after 1 year of follow-up. We are gaining experience with studies in children; current preliminary data from n=7 obese children yield similar mean differences and standard deviations as in adults. Therefore, based upon the change in EELV during constant load exercise in obese men before ( $35 \pm 5$ ) and after ( $39 \pm 3$ ) a loss of 13% of body fat, and the change in RPB during constant load exercise in obese women before ( $4.7 \pm 1.1$ ) and after ( $3.2 \pm 1.6$ ) weight loss, our sample will have sufficient power (.80,  $\alpha=0.05$ ) to detect meaningful paired differences (e.g., 1.5 in RPB) with weight loss and regular exercise. We will retest all children after ~1 yr. We expect less than 10% attrition and repeated data on nearly all children will be available for this Aim. Combining the two obese groups (with and with asthma misdiagnosis), the children will be divided into obese who lost weight, obese who gained weight, and control normal weight children and respiratory changes will be compared between groups with ANOVA as described for Aims 1-3. While these categorized weight changes have clinical appeal, weight change analyzed as a continuous variable may be more powerful and informative. Hence, change at 1 year minus baseline will also be evaluated with Spearman or Pearson correlations to quantify the association between 1-year weight change and the change for respiratory function, exercise tolerance, and DOE variables and, with the 36 obese participants analyzed (by gender), a correlation of 0.45 can be detected with 80% power.

To evaluate gender effects, baseline and follow-up measurements for FRC, peak  $\dot{V}O_2$ , RPB, and EELV will be analyzed in mixed-effects repeated measures models with the study participant included as a random effect. Interactions between gender, study group (obese, obese misdiagnosed with asthma, nonobese), and time can be assessed as fixed effects; weight change effect will be modeled as a covariate. PAQ-C score changes will also be assessed with repeated measures models.

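### Aim 2 would read its expected results as obese children being not deconditioned, but the plan only tests for differences, powers only ml/min/kg, and sets no rule for showing normal percent-predicted peak VO2

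*Combined protocol and SAP*

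**What the plan says.** The hypothesis in Specific Aim 2 has two limbs. Exercise tolerance (peak VO2 in ml/min/kg) is expected to be lower in obese children. Cardiorespiratory fitness (peak VO2 as percent predicted on ideal body weight) is expected to be normal, except in those misdiagnosed with asthma.

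Normal is described in two ways:
- The rationale says that "cardiorespiratory fitness will be within normal limits during graded cycle ergometry", which points to reference values.
- The expected results say that "in comparison with nonobese children, obese children will have decreased exercise tolerance due to increased body weight but normal cardiorespiratory fitness", which points to the control group.

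The interpretation paragraph then states: "We will interpret these results to suggest that obese children are not deconditioned".

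In Statistical Considerations, Aims 1 to 3 are analysed by ANOVA across the three groups within each gender, and "Pairwise group comparisons will be made using least squares means contrasts derived from the linear models". The Aim 2 paragraph names peak VO2 as the primary variable and gives 80% power "to detect a clinically relevant mean difference of 4.7 ml/min/kg for obese versus nonobese children". It gives no SD or power for percent predicted. Under Aim 4, to evaluate gender effects, baseline and follow-up peak VO2 (with FRC, RPB and EELV) "will be analyzed in mixed-effects repeated measures models with the study participant included as a random effect". Percent predicted is not named there either.

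**The concern.** The two limbs need different kinds of evidence. The first is a difference, and a difference test answers it. The second is the absence of a meaningful deficit, which a difference test cannot establish: a contrast can be non-significant because the groups are alike or because the estimate is imprecise. The plan sets no margin, lower limit or interval rule to tell these apart, and its power statement covers the scale on which a deficit is already expected.

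The unsettled comparator adds to this. A comparison with reference values and a comparison with 12 nonobese children differ greatly in precision, so the same true deficit may be evident under one and missed under the other.

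Aims 3 and 4 say how a result contrary to expectation would be read. Aim 2 does not do so for obese children without an asthma misdiagnosis. The protocol regards the Aim 2 message as highly important for providers who prescribe weight loss and exercise, so a real but undetected fitness deficit would matter.

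**Working it through.** **1. The plan's own figure.** Inputs from the Aim 2 paragraph: nonobese 41.9 (SD 4.9), obese boys 26.3 (SD 3.9), detectable difference 4.7. Group sizes of 24 and 12 come from the allocation table; alpha is 0.05, taken as two-sided because sidedness is not stated.
- Unequal variances: SE = √(3.9²/24 + 4.9²/12) = 1.623, df 18.2, noncentrality 4.7/1.623 = 2.90, power 78.2%.
- Equal variances, root-mean-square SD 4.43: SE = 4.43 × √(1/24 + 1/12) = 1.566, noncentrality 3.00, df 34, power 83.1%. With the df-weighted SD of 4.25, power is 86.0%.

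The stated 80% is broadly reproduced. It concerns ml/min/kg, where the preliminary difference is already 41.9 − 26.3 = 15.6.

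**2. The percent-predicted scale.** The documents give no SD, so 10, 12 and 15 points are assumed. True deficits of 10 and 5 points are illustrations.

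P(non-significant) = F(t₀.₉₇₅; df, δ/SE) − F(−t₀.₉₇₅; df, δ/SE), with F the noncentral t distribution function. SE = SD × √(1/n₁ + 1/n₂) for two groups and SD/√n for one group.

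Example, SD 12, 24 vs 12: SE = 12 × 0.3536 = 4.24; critical t 2.032; 10/4.24 = 2.357; P = 0.371.

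| Comparison | 95% CI half-width (SD 10/12/15) | 10-point deficit non-significant | 5-point deficit non-significant |
|---|---|---|---|
| 24 obese vs 12 nonobese, one gender (df 34) | 7.2/8.6/10.8 | 22/37/55% | 72/79/85% |
| 48 vs 24, gender-adjusted (df 69) | 5.0/6.0/7.5 | 2/9/25% | 50/62/74% |
| 24 obese vs reference values (df 23) | 4.2/5.1/6.3 | 0.3/3/12% | 35/50/65% |
| 48 obese vs reference values (df 47) | 2.9/3.5/4.4 | about 0/0/0.5% | 8/19/38% |

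The reference-value rows test the obese mean against 100%. That is a construct for this calculation; the plan speaks of normal limits, which may lie below 100%.

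For instance, at SD 12 an observed within-gender deficit of 7 points has a 95% interval for obese minus nonobese of −7 ± 8.6, or −15.6 to +1.6. It is non-significant, yet compatible with a deficit of 15 points.

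**3. What a confidence-limit rule would do.** Take an illustrative 10-point margin, no true deficit and one-sided 0.025. Power = 1 − F(t₀.₉₇₅; df, 10/SE).
- 24 vs 12: 78/63/45%, so inconclusive 22/37/55% of the time.
- 48 vs 24: 98/91/75%, so inconclusive 2/9/25% of the time.

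Under the rule, a true deficit equal to the margin passes 2.5% of the time.

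**The case against.** The interpretation sentence follows directly on the expected results and is hedged, so it says how those results would be read if obtained. A reader might infer that the conclusion is fixed whatever the data show, or that p > 0.05 will be declared normal. The documents say neither. What stands is narrower: nothing says when the expected result has been obtained, and nothing prevents the non-significance reading.

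The reference-value reading is arguably the more natural one, since percent predicted is already scaled to reference values. On that reading a large deficit would rarely be missed. This is a fair limit on the size of the problem. It does not settle the comparator, because the expected results open with the nonobese group and the planned analysis is a group contrast.

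The SDs, deficits and margin used here are all assumed, and over these inputs the risk runs from about 0 to 85%. The figures therefore show sensitivity to the comparator, not a demonstrated error.

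The contrasts can produce confidence intervals, and the mixed models could give a combined-gender estimate. Both help, but the plan ties neither to percent predicted or to a criterion. That the prediction equation and ideal-weight rule are not named is, by itself, only missing detail.

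**Conclusion.** The concern holds for the second limb of Aim 2. The planned difference contrasts cannot by themselves support a no-deficit conclusion, and the plan has neither a criterion nor a power statement on the percent-predicted scale. A reader might also infer that the Aim 2 power calculation is wrong; it is not, since it is broadly reproducible and matches the first limb.

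Under the assumed SDs of 10 to 15 points, the risk of missing a 10-point deficit is substantial for the planned within-gender contrast with nonobese children (22 to 55%). It is lower with genders combined (2 to 25%) and small against reference values (0.3 to 12% with 24 children, at most about 0.5% with 48). A 5-point deficit is often missed in most configurations, least so with 48 children against reference values (8 to 38%). Nothing in the documents establishes whether 5 points would matter. The analysis of ml/min/kg is unaffected.

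**What to change.** 1. Make percent-predicted peak VO2 an explicit Aim 2 outcome, naming the prediction equation and ideal-weight rule.
2. State which comparator governs the conclusion: reference values or the nonobese group.
3. Report the 95% confidence interval within gender, with a gender-adjusted combined estimate as supportive. Adding percent predicted as an outcome in the planned mixed models would supply the latter.
4. Conclude not deconditioned only if the lower 95% confidence limit lies above a bound that the sponsor justifies in advance. For reference values this is the lower limit of normal; for obese minus nonobese it is minus a margin in percentage points. Otherwise report not shown to differ, inconclusive. A limit of normal meant for an individual child is a lenient test of a group mean, so its choice needs a reason.

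The cost is SAP wording and interval reporting, with no new data. The downside is that even with no true deficit the rule will sometimes be inconclusive, most often within gender against nonobese children. That is a reason to choose the comparator and the bound together, before the data are seen.
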